9.2.1.3. Hepatically Impaired Population

Individuals must have evidence of moderate or severe hepatic impairment, which will be ascertained at index date and in the 12 months before the index date using coded diagnoses and procedures or laboratory values as feasible.

In data sources where laboratory test results are not available, or where there are substantial levels of missingness, individuals will be considered in the target population if they have a diagnosis code that matches the category of moderate or severe hepatic disease according to the CCI revised by Glasheen et al³³ which has been shown to correlate with inpatient admissions and mortality rates. This definition includes but is not limited to:

- Oesophageal varices
- Gastric varices
- Alcoholic hepatic failure
- Toxic liver disease with hepatic necrosis
- Chronic hepatic failure
- Hepatic failure, unspecified
- Hepatic veno-occlusive disease
- Portal hypertension
- Hepatorenal syndrome

In addition, to maximize the inclusion of individuals with moderate or severe hepatic impairment, codes included in the adaptation of the CCI for mild liver disease by Ludvigsson et al²⁵ (e.g., viral hepatitis, autoimmune hepatitis) will be included if they coexist with an ascites code (R18).

In data sources where laboratory results are available (e.g., SIDIAP), severe chronic liver disease can be measured by a MELD score greater than 24.³⁴ The MELD score is calculated using serum bilirubin, serum creatinine, and International Normalized Ratio (INR) by the formula³⁵:

No exact correspondence exists between the Child-Pugh stages and the MELD scores. However, patients with MELD scores equal to or greater than 10 have similar mortality to patients with a Child-Pugh score of less than 10.²⁵ The same score threshold combined with elastography has clear prognosis implications for patients.³⁶ Thus, we propose to include in the study individuals with MELD scores equal to or greater than 10 to include additional individuals with moderate or severe hepatic impairment. Although there have been efforts to derive Child-Pugh scores from electronic healthcare data sources with identifiable rich clinical data,³⁷ those data may not be available in the data sources proposed for this study. PFIZER CONFIDENTIAL

CT24-WI-GL02-RF02 5.0 Non-Interventional Study Protocol Template For Secondary Data Collection Study 01-Aug-2023

```
Page 27 of 72
```

The Child-Pugh score requires data with enough granularity to differentiate clinical levels of severity for ascites and encephalopathy.³⁸ However, in each data source, the additional use of procedural codes or treatments for ascites and encephalopathy will be explored to improve the identification of the target population. Individuals with diagnosis or procedural codes indicating ascites or encephalopathy will be assigned 2 Child-Pugh score points for each clinical sign present (or 4 if they have both signs). The absence of each clinical sign will be assigned 1 point each (or 2 points if neither of the 2 signs are present). Thus, only the presence or absence of ascites and encephalopathy will be evaluated. It will not be possible to evaluate the severity of ascites and encephalopathy; thus, no individuals will be assigned 3 points. However, individuals with a Child-Pugh score of 7 or more will be included in a sensitivity analysis in those data sources with available laboratory results, thereby ensuring that individuals with at least Child-Pugh stage B are included.

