9.7. Data Analysis

Detailed methodology for summary and statistical analyses of data collected in this study will be documented in a SAP, which will be dated, filed, and maintained by the sponsor and PI. The SAP may modify the plans outlined in the protocol; any major modifications of primary endpoint definitions or their analyses will be reflected in a protocol amendment. The SAP will also provide additional detail regarding the evaluation of a threshold of excess risk for each of the outcomes of interest. This will be determined based on background incidences for each event, in addition to prespecified significance level (e.g., alpha = 0.01 or 0.05) and power. All analyses will be conducted using R version R-4.0.3 or higher.⁵⁵

The SAP will contain additional detail of the data analysis and meta-analysis. One interim analysis and report may be conducted. The interim report will be limited to descriptive analyses. Comparative analyses will be included in the final report. Further details will be described in the SAP.

All analyses will be conducted separately for the 3 populations of interest: immunocompromised, renally impaired, or hepatically impaired; and if appropriate, in the combined population. Prior to any combined analysis, a Higgin's I2 statistic will be used to assess the heterogeneity in the primary outcomes across the 3 populations of interest. If the percentage of heterogeneity estimated by I2 is high (e.g., >50%; specific threshold to be specified in the SAP), a combined effect may be estimated using adapted methods such as a random-effects model.

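### Where laboratory results exist, a MELD score of 10 or more alone admits people to the hepatic population, so raised creatinine or INR without liver disease can qualify

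*Protocol*

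**What the plan says.** Protocol section 9.2.1.3 requires evidence of moderate or severe hepatic impairment, established "using coded diagnoses and procedures or laboratory values as feasible". There are two routes in.

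- **Codes.** A diagnosis on the moderate or severe liver disease list is enough. A code from the mild liver disease list counts only when an ascites code is also present.
- **Laboratory values.** "In data sources where laboratory results are available (e.g., SIDIAP), severe chronic liver disease can be measured by a MELD score greater than 24". The section names the score's components as bilirubin, creatinine and INR. It then lowers the bar: "we propose to include in the study individuals with MELD scores equal to or greater than 10", in order to bring in more people with moderate or severe impairment. In support it says "The same score threshold combined with elastography has clear prognosis implications for patients".

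The laboratory route asks for no liver code, no ascites code and no elastography. The source population (section 9.2.3) is everyone registered. The two exclusions (section 9.2.2) concern a prior outcome and a prior RSV vaccination. CKD and warfarin appear in section 9.3.3 as covariates, so such people are expected in the study. The renal definition (section 9.2.1.2) also rests on creatinine, through eGFR below 60.

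For combined analysis, section 9.7 says "a Higgin's I2 statistic will be used to assess the heterogeneity in the primary outcomes across the 3 populations of interest", with a random-effects model as one option if I² is high. No section makes the three populations mutually exclusive.

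**The concern.** Two of the three MELD components are not specific to the liver. Applied to all registered adults aged 60 or over, a threshold of 10 can be met through the kidney or through anticoagulation alone. The code route guards against weak evidence by asking for ascites beside a mild liver code; the laboratory route has no such guard, although section 9.9 expects laboratory data to sharpen the population definitions.

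At stake is whom the hepatic estimate describes. The study exists because safety in hepatically impaired older adults is unknown. If part of the cohort has kidney disease or takes warfarin and has no liver disease, an effect confined to liver disease is diluted, and an effect that arises elsewhere may be reported as hepatic. The label would also mean different things in the data sources that section 9.7.3.3 pools.

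**Working it through.** **Inputs.** From the protocol: the threshold of 10, the three components, the renal cut-off of eGFR 60, the 2021 CKD-EPI equation (section 9.2.1.2) and Table 2. Assumed: the standard MELD form, because the formula is not shown in the text available:

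MELD = 3.78 ln(bilirubin) + 11.2 ln(INR) + 9.57 ln(creatinine) + 6.43, with values below 1 set to 1 and creatinine capped at 4.

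**Step 1: what reaches 10 with the other two values normal.** The terms must supply 10 − 6.43 = 3.57.

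- Creatinine: exp(3.57/9.57) = 1.45 mg/dL
- INR: exp(3.57/11.2) = 1.38
- Bilirubin: exp(3.57/3.78) = 2.57 mg/dL

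If scores are rounded to whole numbers, so that 9.5 counts as 10, the creatinine and INR values become 1.38 mg/dL and 1.32.

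**Step 2: INR alone.** 6.43 + 11.2 ln(INR) gives 14.2 at INR 2.0, 16.7 at 2.5 and 18.7 at 3.0. INR 2.5 together with creatinine 2.5 gives 6.43 + (11.2 + 9.57) × ln 2.5 = 25.5, above even the cut of 24 for severe disease.

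**Step 3: relation to the renal definition.** Creatinine 1.452 in the protocol's CKD-EPI equation at age 70:

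- men: 142 × (1.452/0.9)^−1.2 × 0.9938^70 = 51.7
- women: 142 × (1.452/0.7)^−1.2 × 0.9938^70 × 1.012 = 38.7

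Both lie below 60, so a person who enters on creatinine alone also has an eGFR in the renal range. The reverse is not general. At age 70, with normal INR and bilirubin:

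| eGFR | MELD, men | MELD, women |
|---|---|---|
| 60 | 8.8 | 6.5 |
| 45 | 11.1 | 8.8 |
| 30 | 14.3 | 12.0 |

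Milder CKD does not qualify, and the renal route needs two results at least 90 days apart or another criterion. The overlap is therefore real but partial.

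**Step 4: what dilution could do (illustration only).** Table 2 follows n = (1.960 + 0.842)² × (1 + IRR) / [λ(IRR − 1)²]. For arrhythmia, λ = 0.02 and IRR 2: 7.849 × 3 / 0.02 = 1,178, the printed figure. Suppose a true IRR of 2 exists only in people with liver disease and baseline rates are equal. The observed IRR is then 1 + share × (2 − 1).

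| Share with liver disease (assumed) | Observed IRR | n per cohort |
|---|---|---|
| 100% | 2.0 | 1,178 |
| 50% | 1.5 | 3,925 |
| 20% | 1.2 | 21,585 |

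The protocol gives no counts from which the actual share could be found.

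**Step 5: the I² step.** For three estimates of equal variance with common correlation ρ and no true difference, the expected value of Cochran's Q is 2(1 − ρ) rather than 2. Shared people therefore pull I² downwards. The protocol gives no basis for a value of ρ.

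**The case against.** The strongest reply is that the section demands evidence of hepatic impairment, introduces MELD as a measure of chronic liver disease, and uses it only to add people to a coded core of varices, portal hypertension and hepatic failure. SNDS has no laboratory results, and sources with substantial missingness fall back on codes. A score needs all three tests, and the protocol does not say how many people with CKD have them. Vaccinated and unvaccinated people enter by the same rule, and CKD, chronic liver disease and warfarin are candidate covariates, so different baseline rates in these people do not in themselves bias the rate ratio. A Child-Pugh sensitivity analysis (7 or more) is planned.

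Most of this stands, and it limits the point. It does not remove it: no rule confines MELD to people with known liver disease, weighting balances the two cohorts without making them hepatic, and the Child-Pugh set is only a sensitivity analysis.

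A reader might infer that the threshold contradicts the Child-Pugh rule, because "patients with MELD scores equal to or greater than 10 have similar mortality to patients with a Child-Pugh score of less than 10" takes in scores under 7. The documents do not support that: the same paragraph disclaims exact correspondence between the scales, and the rule of 7 or more belongs to the separate sensitivity analysis.

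A reader might also put a fixed factor, such as √(1 + 2ρ), on the understatement of the combined standard error. That needs a correlation the protocol does not give, and it is a common-effect formula, whereas section 9.7 names random effects only for high I². The combined analysis is itself conditional and may be meant as a union cohort.

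**Conclusion.** The point holds in a limited form. In sources with laboratory results, the rule as written lets creatinine or INR alone place a person without liver disease in the hepatic population. There the population is not specifically hepatic, partly overlaps the renal one, and differs from the code-only population in SNDS. The numerical thresholds (creatinine about 1.45 mg/dL, INR about 1.38) rest on the assumed standard coefficients; the qualitative point rests only on the components that the protocol names.

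Two stronger readings are tempting. One is that the cohort is not hepatic at all: the coded route remains, and the share entering by MELD only cannot be computed. The other is that much of the renal population qualifies as hepatic: at age 70 a woman with eGFR 45, or a man with eGFR just below 60, does not reach 10 on creatinine alone.

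The overlap in the I² step is secondary. It would exist without MELD, and its size is unknown.

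**What to change.** In section 9.2.1.3:

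1. Accept MELD ≥10 only together with a chronic liver disease code, from the mild list already planned or the moderate/severe list.
2. Do not count INR-driven scores in people with warfarin or other vitamin K antagonist records. A workable definition is a score that falls below 10 once INR is set to 1.
3. Report, by data source, how many people qualify by MELD only and how many also meet the renal definition.
4. Keep MELD alone as a sensitivity analysis.

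In section 9.7, run any combined analysis on the union of the three populations with each person counted once per data source, and do not treat the three estimates as independent in the I² step.

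The cost is wording, plus code lists and a covariate already planned. The main analysis loses people with uncoded liver disease and the hepatic cohort shrinks; the sensitivity analysis keeps those people visible. One gap remains: a mild liver code with creatinine raised by kidney disease would still qualify, which the reported renal overlap would show.

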9.2.2. Exclusion Criteria

Patients meeting any of the following criteria will not be included in the study:

- 1. Have a diagnosis for the specific outcome under study within the 12 months prior to the index date (to distinguish the recording of previous events from true new events) and at any time prior to the index date for diabetes type 1
- 2. Have received any RSV vaccinations during the 12-month baseline period

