9.2.1. Inclusion Criteria

Patients meeting the following criteria will be included in the study:

- Vaccinated Cohort: Vaccination with ABRYSVO
- *Unvaccinated Cohort:* No vaccination with ABRYSVO or other vaccines on the index date
- *Unvaccinated Cohort:* No vaccination with any RSV vaccine in the 12-months prior to index
- Each population of immunocompromised or renally impaired or hepatically impaired individuals must meet the population-specific inclusion criteria in Section 9.2.1.1, Section 9.2.1.2, and Section 9.2.1.3, respectively
- Age 60 years and older at index date
- A minimum of 12 months of administrative enrollment history prior to index in one of the selected data sources to ensure adequate characterisation of medical history
- A minimum of one day of follow up post-index
- For analyses of outcomes assessed with the SCRI design, the following additional criteria must be met. Note that the study population for each outcome-specific analysis will thus be different
 - a. Have received ABRYSVO
 - b. Have experienced an event of interest during the risk or control interval
 - c. Have full accrual of data used to define the event in the risk and control intervals combined, after accounting for any data lag and timing of data extraction

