a. Day 0 is the date of vaccine administration (i.e, index date for the vaccinated cohort in the comparative cohort design and SCRI design) or matched index date (for the unvaccinated cohort in the comparative cohort design) b. To align with ongoing postmarketing study C3671031, A Post-Authorization Safety Study of Guillain-Barré Syndrome (GBS) Following ABRYSVOTM Among Older Adults in the United States, sensitivity analyses will be performed for GBS, acute disseminated encephalomyelitis, and transverse myelitis using shorter risk intervals of 1-21 days, 5-28 days, and 1-21 days, respectively. Further details are outlined in Section 9.7.4. c. Published risk and control intervals for demyelinating diseases and cranial disorders were applied to transverse myelitis and narcolepsy/cataplexy.

d. Please note that alternative risk windows were reported in other studies.

e. To align with ongoing postmarketing study C3671037, A Post-Authorization Safety Study of Atrial Fibrillation Following Respiratory Syncytial Virus Vaccine (ABRYSVOTM) Among Older Adults in the

PFIZER CONFIDENTIAL

CT24-WI-GL02-RF02 5.0 Non-Interventional Study Protocol Template For Secondary Data Collection Study 01-Aug-2023

Page 31 of 72

Table 1	List of Select Adverse Events of Special Interest
---------	---

Body system/	Adverse event of special interest	Estimated risk	Analytic Approach
classification		window (days) ^a .	

Veterans Affairs Health System, sensitivity analysis will be performed for atrial fibrillation and supraventricular arrhythmias using a shorter risk interval of 0-3 days. Alternative risk intervals of 0-1 day or 0-30 days may also be considered. Details are provided in Section 9.7.4.

f. Similar risk and control intervals were applied to all cardiovascular and haematological disorders characterised by damage to the blood vessels and/or arteries and clotting (i.e, coagulation disorders and single organ cutaneous vasculitis).

g. Risk intervals for most outcomes start on Day 1 post-index, but for some outcomes, the risk interval starts on the day of vaccination due to biological plausibility of rapid onset following vaccination.

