9.7.4. Sensitivity Analyses

As feasible, sensitivity analyses, as well as analyses to evaluate potential bias, may include, but are not necessarily limited to:

- Comparative cohort design with extended risk windows for the acute outcomes to assess potential outcome under-reporting and misclassification
 - The exception will be atrial fibrillation and supraventricular arrhythmias where shorter risk windows of 0-3 days (as well as 0-1 days and 0-30 days) will be considered to allow for greater consistency with the ongoing ABRYSVO safety study in the Veterans Affairs population (C3671037). Further details on alternative risk intervals will be provided in the SAP.
- SCRI with alternative risk and control intervals to assess potential exposure misclassification. In addition, to allow for greater consistency across ongoing ABRYSVO vaccine safety studies, specifically C3671031 and C3671037, the following risk intervals will be applied as sensitivity analyses for the following AESIs:
 - GBS: risk interval 1-21 days⁵⁹
 - Acute disseminated encephalomyelitis: risk interval 5-28 days ⁶⁰
 - Transverse myelitis: risk interval 1-21 days ^{59, 61}

PFIZER CONFIDENTIAL

CT24-WI-GL02-RF02 5.0 Non-Interventional Study Protocol Template For Secondary Data Collection Study 01-Aug-2023 Page 48 of 72

- A SCRI analysis may also be considered for atrial fibrillation and supraventricular arrhythmias with risk intervals of 0-3 days, 0-1 days and 0-30 days to align with the planned SCRI analysis from study C3671037. Further details on alternative risk and control intervals will be provided in the SAP.
- SCRI with pre-vaccination control interval. If vaccination is deferred while unwell with symptoms related to outcomes, this may violate the assumption of the SCRI design that an outcome event should not alter the probability of subsequent exposure to vaccination. Defining a separate pre-vaccination window can assess these design assumptions and ensure that they are not violated.
- SCRI with a washout period between risk and control intervals, within the subset of outcomes for which an increased risk is detected
- For outcomes with CFR >20%, SCRI analysis incorporating Farrington adjustment or extending follow-up after death for full length of risk and control window
- Use of narrow and broader definition algorithms for outcomes to assess outcome misclassification (comparative cohort and SCRI)

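### Exclusion criterion 1 leaves the optional SCRI with a pre-vaccination control interval with essentially no control events, so it cannot do the check it is listed for

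*Protocol*

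**What the plan says.** Section 9.2.2 opens its list with "Patients meeting any of the following criteria will not be included in the study". Criterion 1 is "Have a diagnosis for the specific outcome under study within the 12 months prior to the index date". The stated reason is to separate re-recorded past events from new ones. For type 1 diabetes the look-back is any time before index.

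Note a to Table 1 (9.3.2.1) fixes the index date for both designs: "Day 0 is the date of vaccine administration (i.e, index date for the vaccinated cohort in the comparative cohort design and SCRI design". Section 9.2.1 adds the SCRI requirements to the general ones ("the following additional criteria must be met"), among them "Have experienced an event of interest during the risk or control interval". Section 9.7.3 says the safety analyses of both designs are run among people who meet the study eligibility criteria.

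The main SCRI (9.1.2, 9.7.3.2) places its control interval after vaccination. Section 9.7.4 lists an alternative, "SCRI with pre-vaccination control interval", because vaccination may be deferred in people unwell with outcome-related symptoms. It says of this: "Defining a separate pre-vaccination window can assess these design assumptions and ensure that they are not violated". The list is introduced by "As feasible, sensitivity analyses, as well as analyses to evaluate potential bias, may include, but are not necessarily limited to". The length and position of the pre-vaccination interval are not given.

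**The concern.** The sensitivity analysis needs people who had the outcome shortly before vaccination, because they supply its control events. Criterion 1 removes those same people. Someone with Guillain-Barré syndrome 30 days before vaccination is a control case for this analysis and is also ineligible for the study.

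What is at stake is the check itself. If vaccination is deferred after an outcome, a shortage of events before vaccination should reveal it. Here the shortage is created by the eligibility rule, so the data would look like complete deferral whether or not any deferral took place.

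**Working it through.** The protocol states no figure for this analysis, so there is none to reproduce. The check compares the two windows and then looks at what the model does with the data that remain.

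**Inputs**
- Exclusion window: 12 months before vaccination, taken as days -365 to -1 (9.2.2; note a to Table 1).
- SCRI risk windows in Table 1: from days 0–1 (anaphylaxis, 2 days) to days 0–42 (generalised convulsion, 43 days). The worked example in 9.1.2 uses 42-day risk and control intervals.
- Model: conditional Poisson regression (9.7.3.2).
- Assumption: the pre-vaccination interval is about as long as the risk window and lies within 12 months before vaccination.
- Illustrative assumption: true rate ratio 1, equal 42-day windows and 20 expected events in each. The protocol gives no expected counts.

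**Step 1: overlap.** An interval of w days that ends the day before vaccination covers days -w to -1. For w from 2 to 43, w < 365, so the interval lies wholly inside the exclusion window. A gap before vaccination changes nothing while w plus the gap stays within 365 days. Each person with an outcome diagnosis in the interval is therefore excluded, and the control count is 0.

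**Step 2: likelihood.** With equal windows, x risk events and 0 control events, the conditional log-likelihood is x·ln[IRR/(1 + IRR)]. For x = 20:

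| IRR | Log-likelihood |
|---|---|
| 1 | -13.86 |
| 10 | -1.91 |
| 100 | -0.199 |
| 10,000 | -0.002 |

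It rises towards 0 without reaching a maximum. There is no finite estimate and no usable Wald interval.

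**Step 3: exact limit.** A lower limit can still be computed. The lower end of the exact two-sided 95% interval for the proportion of events in the risk window is p = 0.025^(1/x), and the limit for the IRR is p/(1 − p).

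| Risk events | p | Lower limit for IRR |
|---|---|---|
| 5 | 0.478 | 0.92 |
| 6 | 0.541 | 1.18 |
| 10 | 0.692 | 2.24 |
| 20 | 0.832 | 4.94 |

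From six risk events upward, the limit exceeds 1 whatever the truth is.

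**Step 4: simulation.** In 2,000 data sets with true IRR 1, none gave a finite IRR when criterion 1 was applied as written. When events in the control interval were not excluded, control events averaged 20.0, all 2,000 estimates were finite and the median IRR was 1.00.

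**Step 5: what could survive.** An interval more than 12 months before vaccination would escape the exclusion, but 9.2.1 guarantees only 12 months of history. Criterion 1 speaks of a diagnosis, while 9.3.2.2 also identifies outcomes from procedures and treatments, so an event with no diagnosis code could remain. Hence the control count is essentially zero, not zero with certainty.

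**The case against.** The analysis is optional: the list in 9.7.4 depends on feasibility and says only what may be included. Section 9.7.4 leaves further detail to the SAP, and 9.7 allows the SAP to modify the plan. Criterion 1 is meant to identify new events, so a programmer might naturally place the clean period before the start of observation. A structural zero for every outcome in every database would also be noticed during the double coding and quality checks of 9.6.2 and 9.8.

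Much of this stands. The flaw is confined to one discretionary analysis, and a corrected or dropped analysis is more likely than a published false signal. The SAP may already handle it. However, the protocol itself fixes eligibility in 9.2.2 without an exception, so this is one stated rule defeating one stated analysis, not detail left for later. More data would not make the analysis feasible while the rule applies.

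A reader might infer that the main SCRI is invalid or left unverified. The documents do not support that. Both intervals of the main SCRI follow vaccination, and an event after vaccination cannot alter a vaccination already given. Deferral mainly threatens the pre-vaccination-control version. Section 9.7.4 also lists other SCRI checks: alternative intervals, a washout period and negative control outcomes.

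**Conclusion.** The contradiction is real but limited. As written, criterion 1 removes essentially all control events from the SCRI with a pre-vaccination control interval, for any interval within 12 months before vaccination. Its IRR would be infinite or spuriously high, and it could not show whether vaccination is deferred after an outcome.

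The conclusion rests on the assumed position of the interval. The counts of 5 to 20 events are illustrations; the direction of the error does not depend on them. The primary cohort analysis and the main SCRI are not affected. Severity is moderate to low.

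**What to change.** Three changes, for this sensitivity analysis only:

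- **9.2.2:** state that criterion 1 applies to the 12 months before the start of the pre-vaccination control interval, not before the index date.
- **9.2.1:** require enrolment history of 12 months plus the length of that interval and any gap between it and vaccination.
- **9.2.4:** either allow look-back data from before 23 August 2022, or accept that the earliest vaccinees drop out of this analysis. The study period now starts exactly 12 months before vaccination became possible. For a 43-day interval with no gap, 365 + 43 = 408 days of history are needed. Within the study period, people vaccinated before 5 October 2023 would not have them.

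The main SCRI and the cohort analysis keep criterion 1 as it stands. The cost is a few sentences, a shifted look-back in the program and the loss of some vaccinees from one sensitivity analysis. That loss is probably small, given at least three vaccination seasons, but the protocol gives no uptake figures from which to size it.
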